Muscle Activity. We will measure muscle activity patterns and activation magnitudes throughout the walking gait cycle using surface electromyography (sEMG) (Noraxon, Scottsdale, AZ). We will measure sEMG from five major muscles of each leg, the biceps femoris (long head), rectus femoris, vastus lateralis, gluteus maximus, and gluteus medius, and three additional muscles of the UL, the soleus, lateral gastrocnemius, and tibialis anterior. Before the experimental sessions, we will prepare the skin over each muscle by shaving, using a mild abrasive, and applying rubbing alcohol. Then, surface electrodes, with a 2cm inter-electrode distance, will be placed on the skin over the muscle belly according to [22]. During each trial, we will record sEMG at 1000 Hz simultaneously with the kinematic and kinetic data. We will process and analyze the raw sEMG data using a band-pass filter (10-500 Hz) and rectify the signal. Then, we will normalize the processed sEMG signals to the peak signal during walking at 1.25 m/s without visual feedback while subjects use their own passive-elastic prosthetic foot to compare each individual to themselves and to minimize individual differences and variability. We will integrate the processed sEMG during the stance and swing phases using trapezoidal integration with a custom software program (Matlab, Mathworks, Natick, MA). Then we will average data across subjects. The processed and integrated sEMG will allow us to compare muscle activity burst magnitude and duration patterns across conditions.

Description of Population to be Enrolled:

We will enroll up to 40 Veterans with unilateral TTAs who are at or above a K3 Medicare functional classification level (MFCL), and who are 18-67 years old and at least 6-months post-amputation from the VA Jewell Clinic, locally, and nationally. Subjects will give informed consent prior to participation. A K3 MFCL means that a person has the ability or potential for ambulation with variable cadence. A person at K3 MFCL is a typical community ambulator who has the ability to traverse most environmental barriers and may have vocational, therapeutic or exercise activity that demands prosthetic use beyond simple locomotion. Subjects will have no known neurological disease or disorder, and will have no musculoskeletal injuries beyond an amputation. These

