We will enforce 5 minutes of rest between trials. During the real-time visual feedback trials, we will ask subjects to match the power magnitude displayed on a computer screen placed in front of them with their AL and/or UL for those 5 minutes. Subjects will be asked to perform a maximum of 35 minutes of walking per day and each experimental session will require ~2 hours of time. The total time commitment for this study is approximately 8 hours; 2 hours per day over 4 days.

D. Description, Risks and Justification of Procedures and Data Collection Tools:

We propose to study healthy people who are familiar with using a prosthesis because this choice minimizes any potential confounding factors associated with novel prosthetic use. Walking requires low exercise intensity, yet poses no more than minimal cardiac risk for this population. We will restrict our patient age range to comply with the American College of Sports Medicine guidelines. The American College of Sports Medicine (ACSM) Guidelines for Exercise Testing and Prescription (Ninth edition, 2014) classify individuals of any age as having low or moderate risk to participate in an exercise program if they present no more than two of the following risk factors: males age \geq 45 yrs, females age \geq 55 yrs, first degree family history of coronary artery disease, cigarette smoking, sedentary lifestyle, obesity, hypertension, dyslipidemia (high cholesterol), and pre-diabetes. These guidelines further recommend that a medical exam and diagnostic exercise testing are not warranted prior to beginning a moderate exercise program for individuals at low to moderate risk. We are being conservative by including patients under 67 years of age (i.e. before their 67th birthday) who do not have any of the other risk factors listed above.

We will comply with Good Clinical Practices (GCPs) by upholding standards for the design, conduct, performance, monitoring, auditing, recording, analysis and reporting of our clinical studies, and by protecting the rights, safety, and well-being of human subjects. We will assure the quality, reliability, and integrity of data collected. We will maintain and monitor GCPs by obtaining Institutional Review Board (IRB)-approval, requiring informed consent, having a data-monitoring plan, reporting Adverse or Serious Adverse Events, having proper documentation, and validating our data collection and reporting procedures.

Foreseeable risks:

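### Is the exercise-risk restriction lost because the population description does not list it?

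*Combined protocol and SAP*

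**What the plan says.** Section IV.D (Description, Risks and Justification of Procedures and Data Collection Tools) opens with "We propose to study healthy people who are familiar with using a prosthesis". It then cites an exercise-testing guideline that puts individuals at low or moderate risk "if they present no more than two of the following risk factors". The list starts with two sex-specific age thresholds and continues with "first degree family history of coronary artery disease, cigarette smoking, sedentary lifestyle, obesity, hypertension, dyslipidemia (high cholesterol), and pre-diabetes". The guideline is reported as advising that "a medical exam and diagnostic exercise testing are not warranted prior to beginning a moderate exercise program for individuals at low to moderate risk". The protocol then sets its own, stricter rule: "We are being conservative by including patients under 67 years of age (i.e. before their 67th birthday"), limited to those "who do not have any of the other risk factors listed above".

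The section headed Description of Population to be Enrolled, also within Section IV, says "We will enroll up to 40 Veterans with unilateral TTAs" and requires a K3 or higher functional level. It describes people "who are 18-67 years old and at least 6-months post-amputation" and asks for no known neurological disease and no other musculoskeletal injury. It calls these items the inclusion and exclusion criteria. It mentions none of the factors in Section IV.D and does not refer to that section.

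Section IV.B adds that a pre-screening form is completed before anyone is enrolled. The form itself is not among the documents.

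**The concern.** A reader expects every eligibility rule to stand in the section that describes who is enrolled. Here one rule stands only in the risk justification. A screener working from the population description alone would not know to ask about smoking, blood pressure, lipids or family history, and nothing in that description limits how many such factors a participant may have.

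The possible cost is to participant safety and consistent screening, not to inference. Section IV.D relies on low or moderate risk status to justify doing without a medical exam and exercise test. If people with three or more factors were enrolled, that justification would not cover them. The age wording adds a small doubt, because a range of 18-67 can be read as including people who are already 67, whereas Section IV.D stops at the 67th birthday.

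**Working it through.** No figure in the plan needs reproducing, so the check is a count and a comparison of the two sections.

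**Count of factors (Section IV.D).** The list has 9 entries. Two are age thresholds (men from 45, women from 55), so 9 − 2 = 7 are non-age factors. I read *other* in the restriction as *other than age*, because the sentence has just set the age limit.

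**Count of criteria (Description of Population to be Enrolled).** Veteran; unilateral transtibial amputation; K3 or above; age 18-67; at least 6 months since amputation; no known neurological disease; no other musculoskeletal injury. That makes 7 criteria. They cover 0 of the 7 non-age factors, and there are 0 cross-references to Section IV.D. The omission is confirmed.

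**Do the sections conflict?** Conflict would require the population description to admit someone whom Section IV.D excludes. It does not say that people with these factors are eligible. Its sentence about recruiting anyone who matches the criteria is a non-discrimination statement and does not make the list exhaustive. One person can satisfy both sections, so they are cumulative. The same holds for age: a person who has not reached the 67th birthday meets both wordings, and the two agree if the range means up to that birthday.

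**Who would fall outside the cited rationale if only the population description were used?** Let *k* be the number of non-age factors and *a* = 1 if the person is past the age threshold for their sex, otherwise 0. The guideline as cited covers a person when *k* + *a* ≤ 2.

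| Non-age factors *k* | Total, *a* = 0 | Total, *a* = 1 | Covered by the cited limit? |
|---|---|---|---|
| 0 (Section IV.D rule) | 0 | 1 | Yes |
| 1 | 1 | 2 | Yes |
| 2 | 2 | 3 | Only if *a* = 0 |
| 3 or more | 3 or more | 4 or more | No |

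Section IV.D's rule therefore leaves a participant with at most 1 factor against a limit of 2. A single missed factor does not take anyone outside the rationale. An example that does go outside it is a man of 50 who smokes and has hypertension: 1 + 1 + 1 = 3.

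**Can the number of such people be estimated?** No. The only related figures are in Section II: 58% of adults without diabetes and 39% with diabetes were physically active, so 100 − 58 = 42% and 100 − 39 = 61% were not. These describe adults in general, not prosthesis users at K3 or above. Inactivity is only a proxy for one factor, and the group at issue has three or more. The documents give no basis for a headcount.

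**Statistical consequences.** The design is repeated-measures within subjects, and the power calculation in Section IV.F uses a paired t-test with 30 participants. Each person serves as their own control. Neither the contrasts nor the inputs to that calculation change with the section in which an eligibility rule is written.

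**The case for a change.** The best argument for acting is that this restriction, together with the age limit, is the only safeguard specific to cardiac risk that the protocol states. The foreseeable risks in Section IV.D cover falls, discomfort from the prosthesis, adhesive irritation, the mouthpiece and confidentiality; none is a cardiac event. The described procedures measure height and weight but do not mention checks of blood pressure, lipids, glucose, smoking or family history. The factors are plausible in this population, because Section II attributes 87-90% of extremity amputations to vascular disease, most often associated with diabetes. Recruitment is local and national in a two-site study, and an amendment would be short.

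Part of this stands. The population description is incomplete on its own, and a cross-reference would be tidier. The documents also cannot show that the pre-screening form carries the restriction.

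It does not establish a defect in the plan. For harm to arise, staff would have to disregard an explicit sentence in the approved protocol, the form would have to omit the restriction, and the person admitted would have to carry three or more factors. None of these is shown. The guideline advice concerns a moderate exercise program, whereas Section IV.D describes the walking as low in intensity with minimal cardiac risk. Rest between trials is enforced, and participants may rest or stop at any time.

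**Conclusion.** The observation is accurate: none of the seven non-age factors in Section IV.D is repeated or cross-referenced in the population description. It does not call for a change. The protocol read as a whole already excludes people with these factors, so repeating the rule elsewhere would leave unchanged who is eligible, the safety rationale and the analysis. It is a gap in placement that study staff fill by applying the protocol they hold. The age wording is a clerical looseness of the same kind.

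This conclusion rests on two assumptions: that screening follows the full protocol, and that the pre-screening form, which is not available here, does not contradict it. If the form were found to omit the factors, the matter would be one of study conduct to correct at the site. The effect on power and on the within-subject comparisons is nil. The number of people who might be misclassified cannot be estimated from the documents.

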Specific Aim 1. Determine the biomechanics and metabolic costs of level-ground walking for 30 Veterans with unilateral TTAs using their own passive-elastic prosthesis both with and without visual feedback training. Each subject will walk at 1.25 m/s on a dual-belt force-measuring treadmill while they use their own passive-elastic prosthetic foot: 1) with no visual feedback, and then with real-time visual feedback targets of: 2) peak propulsive force from the "no feedback" condition, 3) +20% greater peak propulsive force, and 4) +40% greater peak propulsive force. During these visual feedback trials (2-4), we will ask subjects to match the peak propulsive force displayed on a computer monitor (Fig. 1) with their affected leg (AL). We will also ask subjects to: 5) match symmetric visual feedback of the peak propulsive force from both legs. **Hypothesis 1a:** Because passive-elastic prosthetic feet cannot generate power *de novo*, Veterans with TTAs using such prostheses will adopt compensatory biomechanics in their AL and/or unaffected leg (UL) to match the +20% and +40% greater peak propulsive force conditions with their AL and symmetric peak propulsive forces in both legs when using visual feedback during walking, which will increase asymmetry in other values between legs and worsen dynamic stability. Examples of compensatory biomechanics include greater positive joint work and peak joint power in the AL hip joint and/or UL ankle, knee, and hip joints. **Hypothesis 1b:** Due to the negative relation between peak propulsive force and metabolic cost, the metabolic cost of walking when using a passive-elastic prosthesis will be lowest when subjects use visual feedback of +40% peak propulsive force compared to all other conditions. **Hypothesis 1c:** After a 5-min rest period, subjects using their own passive-elastic prosthetic foot will not retain the biomechanics resulting from the prior visual feedback conditions due to compromised stability.

Specific Aim 2. Determine the biomechanics and metabolic costs of level-ground walking for 30 Veterans with unilateral TTAs using a battery-powered ankle-foot prosthesis both with and without visual feedback training. Each subject will walk at 1.25 m/s on a dual-belt force-measuring treadmill while they use a battery-powered ankle-foot prosthesis (emPOWER, BiONX, Ottobock):

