1) with no visual feedback, and then with real-time visual feedback targets of: 2) peak propulsive force from the “no feedback” condition, 3) +20% greater peak propulsive force, and 4) +40% greater peak propulsive force. During these visual feedback trials (2-4), we will ask subjects to match the peak propulsive force displayed on a computer monitor (Fig. 1) with their AL. We will also ask subjects to: 5) match symmetric visual feedback of the peak propulsive force from both legs. **Hypothesis 2a:** Because the emPOWER generates stance-phase prosthetic ankle joint power and net positive work, Veterans with TTAs using the battery-powered prosthesis will be able to match the +20% and +40% greater peak propulsive force conditions with their AL and symmetric peak propulsive forces in both legs without requiring compensatory biomechanics when using visual feedback during walking, which will improve symmetry between legs and dynamic stability. **Hypothesis 2b:** Due to the negative relation between peak propulsive force and metabolic cost, the metabolic cost of walking when using a powered ankle-foot prosthesis will be lowest when subjects use visual feedback of +40% peak propulsive force compared to all other conditions. **H2c:** After a 5-min rest period, subjects will retain the biomechanics resulting from the visual feedback conditions due to improvements in symmetry, metabolic costs, and stability. **Hypothesis 2d:** Veterans with TTAs will have more symmetric biomechanics, lower metabolic costs, and improved dynamic stability when using powered compared to passive-elastic prostheses across all conditions.

II. Background and Significance:

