Metabolic Cost. Each metabolic trial will be five minutes long and at least five minutes of rest will be enforced between trials. We will measure rates of oxygen consumption and carbon dioxide production using indirect calorimetry (ParvoMedics TrueOne 2400, Sandy, UT) and will calculate average steady-state metabolic power (W) from minutes 3-5 of each trial using a standard equation [15]. We will subtract the metabolic power required for standing from the metabolic power required for walking to determine net metabolic power (W/kg). A trial length of five minutes is typically more than adequate for participants to reach steady state metabolic rates. To ensure that we measure metabolic rates during steady-state activity, we will verify all data, and if needed, the trial length will be adjusted. We will minimize day-to-day variability by asking subjects to fast and drink nothing but water at least two hours prior to their experimental session, scheduling sessions at the same time of day, and scheduling sessions that are separated by at least 22 hours and no more than two weeks.

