Days 2, 3 and 4 – Experimental Sessions. We will ask subjects to fast and drink nothing but water for at least 2 hours prior to each experimental session. On each day, we will attach reflective motion capture markers to their legs and pelvis using double-sided tape and Velcro straps, and surface electrodes over their leg muscles using double-sided tape and elastic wraps. We will mark the locations of each electrode with "permanent" marker on their skin. Then, we will ask subjects to walk for 30-60 sec at 1.25 m/s (2.8 mph) using their own prosthesis.

On Days 2, 3, or 4, we will ask subjects to walk at 1.25 m/s on a dual-belt force-measuring treadmill while we measure their metabolic rates, biomechanics, and muscle activity using their own passive-elastic prosthetic foot for:

- 1) 5 min with no visual feedback
- 2) 5 min with real-time visual feedback of affected leg (AL) peak propulsive force from the "no feedback" condition, and 5 min with no visual feedback
- 3) 5 min with real-time visual feedback of +20% greater AL peak propulsive force than the "no feedback" condition, and 5 min with no visual feedback
- 4) 5 min with real-time visual feedback of +40% greater AL peak propulsive force than the "no feedback" condition, and 5 min with no visual feedback
- 5) 5 min with real-time visual feedback of AL peak propulsive force and unaffected leg (UL) peak propulsive force, and 5 min with no visual feedback

On Days 2, 3, or 4, we will ask subjects to walk at 1.25 m/s on a dual-belt force-measuring treadmill while we measure their metabolic rates, biomechanics, and muscle activity using the emPOWER battery-powered ankle-foot prosthesis for:

- 1) 5 min with no visual feedback

- 2) 5 min with real-time visual feedback of AL peak propulsive force from the “no feedback” condition, and 5 min with no visual feedback
- 3) 5 min with real-time visual feedback of +20% greater AL peak propulsive force than the “no feedback” condition, and 5 min with no visual feedback
- 4) 5 min with real-time visual feedback of +40% greater AL peak propulsive force than the “no feedback” condition, and 5 min with no visual feedback
- 5) 5 min with real-time visual feedback of AL peak propulsive force and UL peak propulsive force, and 5 min with no visual feedback

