We have a few potential limitations that could affect the proposed project. Previous studies have found that peak propulsive force is 23-36% lower in the AL when people with a TTA use a passive-elastic prosthesis and is 15-28% lower in the AL when people with a TTA use a powered ankle-foot prosthesis compared to non-amputees [14]. Though it's unlikely, it is conceivable that a subject could elicit more symmetric peak propulsive GRFs. If we find that a subject has a symmetry index for peak propulsive force that is less than 5% during the initial "no feedback" walking trial, we will provide visual feedback of peak propulsive GRFs from both legs at +20% and +40% compared to "no feedback" and will compare the results from these subjects with the overall results from all subjects. It is possible that we will not find significant differences in biomechanics, metabolic costs, or muscle activity with use of targeted visual feedback training of peak propulsive force. However, peak propulsive force has a strong influence on step-to-step transition work and the metabolic cost of walking; therefore, we believe that there will be a significant beneficial effect of real-time visual feedback training. It is also possible that there would be no significant differences between use of passive-elastic versus battery-powered ankle-foot prostheses, but this seems highly unlikely based on previous studies that have compared the use of passive-elastic prosthetic feet to battery-powered ankle-foot prostheses and found significant differences in metabolic cost of transport, step-to-step transition work, and preferred walking speed [11, 14, 23, 24]. Further, though there may be small differences between walking on a treadmill and over-ground walking, we chose to have participants perform experimental trials on a treadmill, which will allow us to control speed while we measure multiple consecutive strides and steady-state metabolic rates, while providing targeted real-time visual feedback. We will then use the results from a treadmill and computer monitor to inform future prosthetic designs that could use a different type of feedback, such as vibration or sound, to provide feedback in a real-world setting. No procedures, situations, or materials are considered to be hazardous to personnel. In addition to improving prosthetic rehabilitation and function, our results could inform the design and control of lower limb prostheses.

F. Data Analysis Plan:

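### Near-symmetric subjects do a two-leg version of the +20% and +40% tasks, are compared with a total that contains them, and have no stated place in the main +20%/+40% contrasts

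*Combined protocol and SAP*

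**What the plan says.** Section I defines +20% and +40% as AL targets. In the feedback trials of Specific Aim 2, subjects are asked to "match the peak propulsive force displayed on a computer monitor (Fig. 1) with their AL", and Aim 1 says the same. The session list for Days 2, 3 and 4 in Section IV.B repeats this, for example "5 min with real-time visual feedback of +20% greater AL peak propulsive force than the" no-feedback condition. Each feedback trial there is followed by a five-minute trial without feedback.

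Section IV.E (Potential Scientific Problems) adds an exception. It calls the situation unlikely but says "it is conceivable that a subject could elicit more symmetric peak propulsive GRFs". If SI for peak propulsive force is under 5% in the initial no-feedback trial, "we will provide visual feedback of peak propulsive GRFs from both legs at +20% and +40" percent relative to no feedback. The plan then "will compare the results from these subjects with the overall results from all subjects".

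Section IV.F (Data Analysis Plan) contains power calculations only and does not mention these subjects. Two other statements bear on what can be fitted into a session. Section IV.B says "Subjects will be asked to perform a maximum of 35 minutes of walking per day". The Metabolic Cost text in Section IV.A says "if needed, the trial length will be adjusted", in the context of reaching steady state.

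**The concern.** There are two separate problems.

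- **Comparator.** Comparing a subgroup with a total that contains it pulls the difference toward zero. The two sides also differ in task as well as in baseline symmetry.
- **Pooling.** The plan does not say whether the two-leg trials enter the +20% and +40% contrasts. If they do, one label covers two tasks. H1b and H2b turn on the +40% condition, H1a and H2a involve symmetry, and H1c and H2c use the no-feedback trials that follow. H2d compares prostheses across all conditions. The rule does not say whether SI is judged separately for each prosthesis. If it is, one subject could do the two-leg task on one device and the AL-only task on the other.

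A rule that changes what a subject does needs a matching analysis rule, fixed before the data are seen.

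**Working it through.** The plan states no figure on this point, so there is none to reproduce. The number of near-symmetric subjects, k, is not given; the values below are assumptions. The sample size n is 30 in Sections I and IV.F, and the population description allows up to 40 enrolled.

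**1. Subgroup against a total that contains it.** Let S be the subgroup mean and R the mean of the other subjects.

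- Total mean = [kS + (n-k)R]/n.
- S - total mean = (1 - k/n)(S - R), so the shrinkage is k/n.
- n=30, k=1: 1/30 = 3.3%.
- n=30, k=3: 3/30 = 10%.
- n=40, k=3: 3/40 = 7.5%.

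This applies to a difference in means.

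**2. Effect of pooling on propulsive-force SI.** Section IV.A defines SI = |UL - AL| / [0.5(UL + AL)] x 100. Assume a subject with UL = AL = 1 at baseline who meets the target exactly, with UL unchanged in the AL-only task.

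| Condition | AL-only task | Two-leg task |
|---|---|---|
| +20% | 0.2/1.1 x 100 = 18.2% | (1.2 - 1.2)/1.2 x 100 = 0% |
| +40% | 0.4/1.2 x 100 = 33.3% | (1.4 - 1.4)/1.4 x 100 = 0% |

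With k=3 of 30, the mean SI differs between the two versions by 3/30 x 18.2 = 1.8 points at +20% and 3/30 x 33.3 = 3.3 points at +40%. This variable was chosen because the task itself fixes its value. For metabolic cost, joint work or angular momentum, the documents give nothing from which to derive a size or a direction.

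**3. Replace or add?** Per prosthesis, the session list has 1 + 4 x 2 = 9 five-minute trials (45 min). Two prostheses give 18 trials (90 min). The cap over three experimental days is 3 x 35 = 105 min.

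- Each of Days 2 to 4 opens with a 30-60 s walk. If it counts toward the cap, seven trials need 7 x 5 + 0.5 = 35.5 min or more, which exceeds 35. Six fit per day, or 18 in three days, exactly the number scheduled. Nothing can be added.
- If the opening walk does not count, 21 trials fit. Two extra feedback trials for one prosthesis make 20 (100 min), which fits. Two for each prosthesis make 22 (110 min), which does not. Two with their follow-on trials for one prosthesis also make 22 and do not fit.

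**4. Precision.** Leaving k subjects out of a condition multiplies the standard error by about sqrt[30/(30-k)]: sqrt(30/29) = 1.017 for k=1 and sqrt(30/27) = 1.054 for k=3. A comparison of 3 with 27 subjects (two-sample t-test, two-sided alpha 0.05, 80% power) detects only about 1.8 SD, so it can only be descriptive.

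**The case against.** The plan can be defended on several grounds.

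- Setting an unusual subgroup beside the overall result is a common descriptive display. The plan attaches no test to it, no hypothesis depends on it, and the phrase about all subjects may loosely mean the main results. This stands as a reason for low weight. It does not remove the overlap in the wording.
- The two tasks are not wholly different, because the AL target is still +20% or +40% above the subject's own no-feedback value. That is correct and limits the effect on AL outcomes. It does not protect between-leg outcomes, as the SI example shows.
- The silence about pooling is partly a symptom of a wider gap, since Section IV.F names no model for any feedback contrast. That is fair. Here, however, there is a stated rule that changes the task and a stated comparison, and both can be repaired directly.
- The case is expected to be rare and may not arise. This also stands.

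Two stronger readings are tempting and go beyond the documents. A reader might infer that the main +20%/+40% results are materially biased. The documents do not say that the trials are pooled, and they give neither a count of such subjects nor a spread for SI. A reader might also infer that the walking cap proves replacement. It makes replacement the natural reading, but the plan does not say whether the opening walk counts, and it lets trial length be adjusted.

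**Conclusion.** The point holds as a minor one. As worded, the comparator contains the subgroup, and a difference in means is understated by k/n. The treatment of the two-leg trials in the main contrasts, and in the no-feedback trials that follow them, is not stated. If they are pooled, the shift in mean propulsive-force SI is of the order of 2 to 3 points for three such subjects in 30. That figure assumes exact baseline symmetry, targets met exactly, and UL unchanged in the AL-only task. With no near-symmetric subjects there is no effect. The direction of any effect on other outcomes is unknown.

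**What to change.** 1. Compare SI<5% subjects with the remaining SI>=5% subjects instead of with everyone. Present this descriptively, and note that task and baseline symmetry are confounded.
2. Code the two-leg +20%/+40% trials, and the no-feedback trials that follow them, separately from the AL-only conditions. Report the +20%/+40% contrasts, including H2d, with and without them, and name the main version in advance.
3. Reconcile Section IV.E with Specific Aims 1 and 2 and with the session list and walking cap in Section IV.B, so that it is clear whether the two-leg trials replace or add to the AL-only trials.

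The first two items are analysis wording; the third is a short protocol clarification. No new subjects are needed. Where the trials are left out, standard errors widen by about 1.7% (k=1) or 5.4% (k=3) at n=30. The estimate then applies to subjects with SI of 5% or more, and the conditions no longer contain the same set of subjects. Reporting both versions limits this.
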